6.7.4. Vital Signs

Vital signs will be measured at the time points indicated in the study procedures table ([Appendix 2](#)).

Vital signs should be taken after the subject has been resting for 5 min and will include heart rate, respiratory rate, SBP, DBP, and body temperature.

6.7.5. Physical Examination

A physical examination should be performed at the time points indicated in the study procedures table ([Appendix 2](#)).

Any changes from the Day 1 will be recorded. Height should be measured at Screening only.

At Screening, Week 24 and Week 52 (or at ET), a complete physical examination should be performed. Symptom-driven physical exams should be performed at all other visits. Weight is measured at all visits.

6.7.6. Other Safety Assessments

6.7.6.1. 12-lead Electrocardiogram

A resting 12-lead ECG will be performed at the time points indicated in the study procedures table ([Appendix 2](#)).

The ECG should be obtained after the subject has been resting in the supine position for 5 min and will include heart rate (HR), R-R interval, QRS, uncorrected QT, morphology, and rhythm analysis. QT interval corrected for HR according to Fridericia (QTcF) will be derived during the statistical analysis. ECGs will be interpreted by the investigator for clinical significance and results will be entered into the eCRF.

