Criteria for Evaluation:

Safety: Safety will be assessed by documentation of AEs, clinical laboratory tests, physical examinations, vital signs, and 12-lead ECGs during the study.

Efficacy: The primary endpoint is:

- The proportion of subjects who achieve an ACR20 response at Week 24.

The key secondary endpoints are:

- Change from Baseline in the HAQ-DI score at Week 24
- The proportion of subjects who achieve DAS28 [CRP]<2.6 at Week 24
- Change from Baseline in mTSS at Week 24

Pharmacokinetics: Plasma concentrations of filgotinib and the active metabolite (GS-829845) will be analyzed.

Statistical Methods:

The primary analysis set for efficacy analyses will be the Full Analysis Set (FAS), which includes all randomized subjects who received at least one dose of study drug.

The primary endpoint is the proportion of subjects who achieve an ACR20 response at Week 24. The primary analysis will consist of a superiority test of filgotinib 200 mg in combination with MTX compared to MTX alone based on the ACR20 response rates at Week 24. Cochran-Mantel-Haenszel approach adjusting for the stratification factors will be used for the hypothesis testing at the 2-sided 0.05-level.

The following hypothesis testing will commence after the primary analysis reaches statistical significance, and will be tested according to the hierarchical testing principle at the 2-sided 0.05 level. If a null hypothesis is not rejected, formal sequential testing will be stopped and only nominal significance will be reported for the remaining key secondary hypotheses.

- 1) Superiority of filgotinib 200 mg in combination with MTX compared to MTX alone based on the change from Baseline in HAQ-DI at Week 24
- 2) Superiority of filgotinib 200 mg in combination with MTX compared to MTX alone based on the response rate of DAS28 (CRP)<2.6 at Week 24
- 3) Superiority of filgotinib 100 mg in combination with MTX compared to MTX alone based on ACR20 response rate at Week 24
- 4) Superiority of filgotinib 100 mg in combination with MTX compared to MTX alone based on the change from Baseline in HAQ-DI at Week 24
- 5) Superiority of filgotinib 100 mg in combination with MTX compared to MTX alone based on the response rate of DAS28<2.6 at Week 24
- 6) Superiority of filgotinib 200 mg alone compared to MTX alone based on ACR20 response rate at Week 24
- 7) Superiority of filgotinib 200 mg alone compared to MTX alone based on the change from Baseline in HAQ-DI at Week 24

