- 8) Superiority of filgotinib 200 mg alone compared to MTX alone based on the response rate of DAS28 (CRP)<2.6 at Week 24
- 9) Superiority of filgotinib 200 mg in combination with MTX compared to MTX alone based on the change from Baseline in mTSS at Week 24

10) Superiority of filgotinib 100 mg in combination with MTX compared to MTX alone based on the change from Baseline in mTSS at Week 24

11) Superiority of filgotinib 200 mg alone compared to MTX alone based on the change from Baseline in mTSS at Week 24

All continuous endpoints will be summarized using an 8-number summary (n, mean, standard deviation [SD], median, 1st quartile [Q1], 3rd quartile [Q3], minimum, maximum) by treatment group. All categorical endpoints will be summarized by the number and percentage of subjects who meet the endpoint definition.

Safety endpoints will be analyzed by the number and percent of subjects with events or abnormalities for categorical values or 8-number summary (n, mean, SD, median, Q1, Q3, minimum, maximum) for continuous data by treatment group.

Sample size is determined based on the superiority test of filgotinib 200 mg in combination with MTX compared to MTX alone based on the change from Baseline in mTSS at Week 24. When assuming a difference of 0.62 between the two groups and a common standard deviation of 2.7, 400 subjects in the filgotinib 200 mg in combination with MTX group and 400 in the MTX alone group are required to obtain 90% power at a 2-sided 0.05-level.

The total sample size will be 1200 (400 subjects for filgotinib 200 mg in combination with MTX group, 200 subjects for filgotinib 100 mg in combination with MTX group, 200 subjects for filgotinib 200 mg alone group and 400 subjects for MTX alone group). This sample size will provide over 90% power to detect an increase in ACR20 response rate of 62% to 78% between the MTX alone group and each of the filgotinib groups respectively, using a 2-sided 0.05-level test.

This study will be conducted in accordance with the guidelines of Good Clinical Practice (GCP) including archiving of essential documents.

GLOSSARY OF ABBREVIATIONS AND DEFINITION OF TERMS

Ab	antibody
ACPA	anti-citrullinated protein antibody
ACR X	American College of Rheumatology X% improvement
AE	adverse event
ALT	alanine aminotransferase
ANA	anti-nuclear antibody
aPTT	activated partial thromboplastin time
ATP	adenosine triphosphate
AST	aspartate aminotransferase

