PBMC	peripheral blood mononuclear cells
PD	pharmacodynamics

PK	pharmacokinetics
PP	per-protocol
PT	prothrombin time
PTM	placebo to match
q.d.	quaque die ; once daily
RA	rheumatoid arthritis
RAMRIS	rheumatoid arthritis magnetic resonance imaging score
RF	rheumatoid factor
SAE	serious adverse event
SAP	Statistical Analysis Plan
SBP	systolic blood pressure
s.c.	subcutaneous
SD	standard deviation
SDAI	Simplified Diagnostic Activity Index
SF-36	short-form health survey, 36 questions
SI	international system of units
SJC66	swollen joint count based on 66 joints
TB	tuberculosis
TEAEs	treatment emergent adverse events
TJC68	tender joint count based on 68 joints
t_{\max}	the time of occurrence of maximum observed plasma concentration
TNFi	tumor necrosis factor inhibitors
TNF α	tumor necrosis factor α
TSQM	Treatment Satisfaction Questionnaire for Medication
UGTs	uridine 5'disphosphate glucuronosyltransferases
ULN	upper limit of normal
US	United States
vfpBMCs	viably frozen peripheral blood mononuclear cells
vs.	versus
WBC	white blood cell
WPAI-RA	Work Productivity and Activity Impairment for Rheumatoid Arthritis

Definition of Terms

QTcF	QT interval corrected for HR according to Fridericia's formula: $QTcF = QT / (RR)^{(1/3)}$, where $RR = 60/HR$ RR = RR interval in seconds HR = heart rate in beats per minute
------	--

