8.6. Safety Analysis

All safety analyses will be performed using the safety analysis set.

Safety will be evaluated by assessment of clinical laboratory tests, physical examinations, vital signs measurements at various time points during the study, and by the documentation of AEs.

All safety data collected on or after the first dose of study drug administration up to 30 days after the last dose of study drug, unless specified otherwise will be summarized by treatment group according to the study drug received.

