## **7.5. Electrocardiogram Results**

### **7.5.1. Investigator Electrocardiogram Assessment**

A shift table of the investigators' assessment of ECG results at each visit compared with baseline values will be presented by treatment group using the following categories: normal; abnormal (not clinically significant); abnormal (clinically significant); or missing. The number and percentage of subjects in each cross-classification group of the shift table will be presented. Subjects with a missing value at baseline or postbaseline will not be included in the denominator for percentage calculation.

No formal statistical testing is planned.

A by-subject listing for ECG assessment results will be provided by subject ID number and visit in chronological order.

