## **7.7. Changes From Protocol-Specified Safety Analyses**

There are no deviations from the protocol-specified safety analyses.

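### The protocol commits to deriving QTcF in the analysis, but the SAP plans no numeric QT output and records no change

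*Protocol*

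**What the plan says.** **Protocol.** Section 6.7.6.1 (12-lead Electrocardiogram) says the recording will include "heart rate (HR), R-R interval, QRS, uncorrected QT, morphology, and rhythm analysis", and then that "QT interval corrected for HR according to Fridericia (QTcF) will be derived during the statistical analysis". The Definition of Terms in the glossary has an entry for QTcF ("QT interval corrected for HR according to Fridericia's formula"): QTcF = QT/(RR)^(1/3), with RR = 60/HR in seconds. The synopsis, under Criteria for Evaluation, says "Safety will be assessed by documentation of AEs, clinical laboratory tests, physical examinations, vital signs, and 12-lead ECGs during the study". Under Statistical Methods it gives safety endpoints counts and percentages if categorical, and otherwise an "8-number summary (n, mean, SD, median, Q1, Q3, minimum, maximum) for continuous data by treatment group". Section 8.6 is narrower: "Safety will be evaluated by assessment of clinical laboratory tests, physical examinations, vital signs measurements at various time points during the study", together with AEs. It does not mention ECGs.

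**SAP.** Section 7.5 has a single subsection, 7.5.1, which plans a shift table in which the investigator's "assessment of ECG results at each visit compared with baseline values will be presented by treatment group". The categories are normal, two grades of abnormal (by clinical significance) and missing, and a by-subject listing of the ECG assessments is added. Section 3.8.2 gives ECG visit windows (Table 3-2) and a separate post-treatment window. Section 7.7 reads: "There are no deviations from the protocol-specified safety analyses".

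**The concern.** A protocol commitment to derive a named safety variable has no counterpart in the document that specifies the analysis, and the section meant to record such departures says there are none. A programmer working from the SAP alone would produce no QTcF values.

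What is lost is resolution. A normal/abnormal reading made subject by subject is not built to show a modest shift in mean QTcF between arms; a summary of value and change from baseline is. If QTcF is later computed because someone asks for it, the analysis will be post hoc, with its baseline, windows and summaries chosen after unblinding.

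**Working it through.** The documents give no figure to reproduce and no calculation applies. The check is a comparison of texts.

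| Question | Protocol | SAP |
|---|---|---|
| Is QTcF to be derived? | Yes, unconditionally (6.7.6.1) | Not mentioned |
| Is a formula given? | Yes (Definition of Terms) | No |
| Are the inputs obtained? | HR, R-R and uncorrected QT are part of the recording (6.7.6.1) | No interval parameter named |
| Is ECG a safety criterion? | Yes in the synopsis; not listed in 8.6 | Yes, through 7.5 |
| What output is planned? | 8-number summary for continuous safety data (synopsis) | Categorical shift table and listing (7.5.1) |
| Is a change declared? | Not applicable | None (7.7) |

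1. *Is the commitment real?* The wording in 6.7.6.1 is unconditional and places the derivation in the statistical analysis. The formula needs only QT and either RR or HR.

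2. *Is QTcF elsewhere in the SAP?* QT, QTc, QTcF, Fridericia, RR and QRS appear nowhere in it. The abbreviation list contains ventricular rate, but the text never uses it. Table 3-2 and the post-treatment paragraph of 3.8.2 refer to ECG data without naming a parameter.

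3. *Could the text be blacked out?* Neither SAP 7.5 nor its entry in the table of contents carries a redaction mark.

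4. *Does the sponsor use these sections to record changes?* Yes. SAP 6.5 lists and justifies the efficacy changes: the move from Cochran-Mantel-Haenszel to logistic regression, the two added key secondary endpoints and the reordered hierarchy. Section 7.7 is the safety counterpart.

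5. *Would the existing conventions support the analysis?* Yes. ECGs are scheduled at Screening, Weeks 12, 24, 36 and 52 or ET, and Post Treatment Week 4. Under SAP 3.8.2 the last value on or before first dose is baseline, which would normally be the Screening ECG. Table 3-2 covers Weeks 12, 24, 36 and 52 on treatment. It does not cover the follow-up ECG, which falls in the window from last dose + 8 days to last dose + 30 days in the same section.

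**The case against.** **SAP 7.7 may be right on a narrow reading.** It refers to protocol-specified safety analyses. The protocol's own Safety Analysis section (8.6) lists neither ECG nor QTcF, and 6.7.6.1 promises a derivation without naming a table. This stands in part: 7.7 is inconsistent with 6.7.6.1 and the synopsis, but a reader who infers that it is plainly false goes too far. The narrow reading does not remove the inconsistency. The derivation itself is promised, and the SAP already analyses ECGs although 8.6 is silent on them.

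**The SAP is silent rather than prohibitive.** SAP 3 prescribes descriptive statistics for continuous variables, and 3.8.2 says follow-up ECGs are to be summarised and has a rule for averaging tied continuous values. A reader might infer from the gap that the trial cannot say anything quantitative about QT. The documents do not support that, because QTcF could be computed later if the intervals are held. What is missing is a pre-specified analysis; the general lines name no ECG parameter and do not supply one.

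**The numeric data may not be in the database.** Section 6.7.6.1 says results go into the eCRF, but does not make clear whether that means intervals or only the interpretation. This stands and has to be checked first.

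**Earlier evidence is reassuring.** Protocol 1.2.2.2 reports no relevant ECG or QT effects nonclinically, and 1.4 no clinically relevant ECG impact in Phase 1 and 2. This supports a low ranking for the point, but does not withdraw the commitment. Section 1.2.2.2 also notes a slight heart-rate increase with the metabolite at 7 times the clinical Cmax, which is a reason to prefer a rate-corrected measure.

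**Conclusion.** The point holds as an inconsistency between protocol and SAP, with one practical result: no quantitative QT analysis is pre-specified. It is minor. QTcF enters no endpoint, no tested hypothesis and none of the discontinuation criteria in Protocol 3.5.2, and investigator review of ECGs continues.

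Two further inferences should be resisted. One is to size the problem by scheduled ECGs: 1200 subjects x 5 post-baseline times = 6,000. That is only a ceiling, since early terminators miss later visits and subjects entering the LTE have no follow-up visit, and a count of recordings says nothing about a missed signal. The other is that the protocol requires tables of QTcF outliers; it names no thresholds.

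The conclusion assumes that the protocol text at hand is the version the SAP says it is based on (Amendment 1, 05 July 2016). That the numeric intervals were captured is not established; it bears on the remedy, not on the inconsistency.

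**What to change.** First confirm that QT and HR or RR values are in the database. Then do one of the following.

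- **Derive it.** Add to SAP 7.5: QTcF = QT/(RR)^(1/3) with RR = 60/HR, and an 8-number summary of value and change from baseline by treatment group and visit in the Safety Analysis Set. Use the Table 3-2 windows on treatment and the post-treatment window of SAP 3.8.2 for the follow-up ECG.
- **Do not derive it.** Correct SAP 7.7 to record that QTcF will not be derived, as a change from Protocol 6.7.6.1, with the reason. The same applies if the intervals turn out not to be held.

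The first option costs one extra descriptive table, provided the values are already held; the second costs a sentence or two. Neither changes the efficacy analyses.

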6.8. Pharmacokinetics Assessments

For all subjects, blood samples for PK analysis will be collected at least 30 minutes post study drug dosing at Week 4, prior to study drug dose at Week 12 and Week 24, and at Week 52 or ET.

CCI

Plasma concentrations of filgotinib and GS-829845 will be analyzed.

Additional analyses (e.g., for MTX and its metabolites) may be performed.

6.9. Biomarker Assessments

Blood and urine samples for biomarker analysis will be collected at Day 1, Weeks 4, 8, 12, 24, 36, and Week 52 or ET for assessment of markers including but not limited to inflammation, immune status, joint damage, and the JAK-STAT pathway. CCI

Specific information regarding the collection and processing of biomarker samples (if applicable) will be provide to each site in a separate laboratory manual.

7. ADVERSE EVENTS AND TOXICITY MANAGEMENT

7.1. Definitions of Adverse Events, Adverse Reactions, and Serious Adverse Events

7.1.1. Adverse Events

An adverse event (AE) is any untoward medical occurrence in a clinical study subject administered a medicinal product, which does not necessarily have a causal relationship with the treatment. An AE can therefore be any unfavorable and/or unintended sign, symptom, or disease temporally associated with the use of a medicinal product, whether or not considered related to the medicinal product. AEs may also include pre- or post-treatment complications that occur as a result of protocol specified procedures, lack of efficacy, overdose, drug abuse/misuse reports, or occupational exposure. Preexisting events that increase in severity or change in nature during or as a consequence of participation in the clinical study will also be considered AEs.

An AE does not include the following:

- Medical or surgical procedures such as surgery, endoscopy, tooth extraction, and transfusion. The condition that led to the procedure may be an adverse event and must be reported.
- Pre-existing diseases, conditions, or laboratory abnormalities present or detected before the screening visit that do not worsen.
- Situations where an untoward medical occurrence has not occurred (eg, hospitalization for elective surgery, social and/or convenience admissions)
- Overdose without clinical sequelae (see Section 7.7.1)
- Any medical condition or clinically significant laboratory abnormality with an onset date before the consent form is signed and not related to a protocol-associated procedure. It is considered to be pre-existing and should be documented on the medical history CRF.

7.1.2. Serious Adverse Events

A **serious adverse event** (SAE) is defined as an event that, at any dose, results in the following:

- Death
- Life-threatening (Note: The term “life-threatening” in the definition of “serious” refers to an event in which the subject was at risk of death at the time of the event; it does not refer to an event that hypothetically might have caused death if it were more severe.)
- In-patient hospitalization or prolongation of existing hospitalization

- Persistent or significant disability/incapacity
- A congenital anomaly/birth defect
- A medically important event or reaction: such events may not be immediately life-threatening or result in death or hospitalization but may jeopardize the subject or may require intervention to prevent one of the other outcomes constituting SAEs. Medical and scientific judgment must be exercised to determine whether such an event is a reportable under expedited reporting rules. Examples of medically important events include intensive treatment in an emergency room or at home for allergic bronchospasm; blood dyscrasias or convulsions that do not result in hospitalization; and development of drug dependency or drug abuse. For the avoidance of doubt, infections resulting from contaminated medicinal product will be considered a medically important event and subject to expedited reporting requirements.

7.1.3. Clinical Laboratory Abnormalities and Other Abnormal Assessments as Adverse Events or Serious Adverse Events

Laboratory abnormalities without clinical significance are not to be recorded as AEs or SAEs. However, laboratory abnormalities (e.g., clinical chemistry, hematology, and urinalysis) that require medical or surgical intervention or lead to IMP interruption, modification, or discontinuation must be recorded as an AE, as well as an SAE, if applicable. In addition, laboratory or other abnormal assessments (e.g., electrocardiogram, x-rays, vital signs) that are associated with signs and/or symptoms must be recorded as an AE or SAE if they meet the definition of an AE or SAE as described in Sections 7.1.1 and 7.1.2. If the laboratory abnormality is part of a syndrome, record the syndrome or diagnosis (e.g., anemia), not the laboratory result (i.e., decreased hemoglobin).

For specific information on handling of clinical laboratory abnormalities in this study, please refer to Section 7.5.

7.2. Assessment of Adverse Events and Serious Adverse Events

The investigator or qualified subinvestigator is responsible for assessing AEs and SAEs for causality and severity, and for final review and confirmation of accuracy of event information and assessments.

7.2.1. Assessment of Causality for Study Drugs and Procedures

The investigator or qualified subinvestigator is responsible for assessing the relationship to IMP therapy using clinical judgment and the following considerations:

- **No:** Evidence exists that the adverse event has an etiology other than the IMP. For SAEs, an alternative causality must be provided (e.g., pre-existing condition, underlying disease, intercurrent illness, or concomitant medication).
- **Yes:** There is reasonable possibility that the event may have been caused by the investigational medicinal product.

It should be emphasized that ineffective treatment should not be considered as causally related in the context of adverse event reporting.

The relationship to study procedures (e.g., invasive procedures such as venipuncture or biopsy) should be assessed using the following considerations:

- **No:** Evidence exists that the adverse event has an etiology other than the study procedure.
- **Yes:** The adverse event occurred as a result of protocol procedures, (eg., venipuncture)

7.2.2. Assessment of Severity

The severity of AEs will be graded using the modified CTCAE, version 4.03. For each episode, the highest grade attained should be reported.

If a CTCAE criterion does not exist, the investigator should use the grade or adjectives: Grade 1 (mild), Grade 2 (moderate), Grade 3 (severe), Grade 4 (life-threatening) or Grade 5 (fatal) to describe the maximum intensity of the adverse event. For purposes of consistency with the CTCAE, these intensity grades are defined in [Table 7-1](#) and [Appendix 4](#).

Table 7-1. Grading of Adverse Event Severity

Grade	Adjective	Description
Grade 1	Mild	Asymptomatic or mild symptoms; clinical or diagnostic observations only; intervention not indicated
Grade 2	Moderate	Local or noninvasive intervention indicated; limiting age-appropriate instrumental ADL
Grade 3	Severe	Severe or medically significant but not immediately life-threatening; hospitalization or prolongation of hospitalization indicated; disabling; limiting self-care ADL
Grade 4	Life-threatening	Urgent intervention indicated
Grade 5	Death	Death related AE

* Activities of Daily Living (ADL) Instrumental ADL refer to opening preparing meals, shopping for groceries or clothes, using the telephone, managing money, etc.

7.3. Investigator Requirements and Instructions for Reporting Adverse Events and Serious Adverse Events to Gilead

Requirements for collection prior to study drug initiation:

After informed consent, but prior to initiation of study medication, the following types of events should be reported on the case report form (eCRF): all SAEs and adverse events related to protocol-mandated procedures.

Adverse Events

Following initiation of study medication, collect all AEs, regardless of cause or relationship, until 30-days after last administration of study IMP must be reported to the eCRF database as instructed.

All AEs should be followed up until resolution or until the adverse event is stable, if possible. Gilead Sciences may request that certain AEs be followed beyond the protocol defined follow up period.

Serious Adverse Events

All SAEs, regardless of cause or relationship, that occurs after the subject first consents to participate in the study (ie, signing the informed consent) and throughout the duration of the study, including the protocol-required post treatment follow-up period, must be reported to the eCRF database and Gilead Drug Safety and Public Health (DSPH) as instructed. This also includes any SAEs resulting from protocol-associated procedures performed after informed consent is signed.

Any SAEs and deaths that occur after the post treatment follow-up visit but within 30-days of the last dose of study IMP, regardless of causality, should also be reported.

Investigators are not obligated to actively seek SAEs after the protocol defined follow up period however, if the investigator learns of any SAEs that occur after study participation has concluded and the event is deemed relevant to the use of IMP, he/she should promptly document and report the event to Gilead DSPH.

- All AEs and SAEs will be recorded in the eCRF database within the timelines outlined in the eCRF completion guideline.

Electronic Serious Adverse Event (eSAE) Reporting Process

- Site personnel record all SAE data in the eCRF database and from there transmit the SAE information to Gilead DSPH within 24 hours of the investigator's knowledge of the event. Detailed instructions can be found in the eCRF completion guidelines.
- If for any reason it is not possible to record the SAE information electronically, ie, the eCRF database is not functioning, record the SAE on the paper serious adverse event reporting form and submit within 24 hours as described above.

Gilead DSPH: Fax: PPD [REDACTED]
E-mail: PPD [REDACTED]

- As soon as it is possible to do so, any SAE reported via paper must be transcribed into the eCRF Database according to instructions in the eCRF completion guidelines.
- If an SAE has been reported via a paper form because the eCRF database has been locked, no further action is necessary.

- All AEs and SAEs will be recorded in the eCRF database within the timelines outlined in the eCRF completion guideline.
- For fatal or life-threatening events, copies of hospital case reports, autopsy reports, and other documents are also to be submitted by e-mail or fax when requested and applicable. Transmission of such documents should occur without personal subject identification, maintaining the traceability of a document to the subject identifiers.
- Additional information may be requested to ensure the timely completion of accurate safety reports.
- Any medications necessary for treatment of the SAE must be recorded onto the concomitant medication section of the subject's eCRF and the event description section of the SAE form.

